3.3 Rationale for dose/regimen, route of administration and duration of treatment

As mentioned in [Section 1.1](#) and [Section 3.2](#), KAE609 has been evaluated in single dose up to 75 mg and repeated dose up to 30 mg (3 day-QD) in malaria patients. It has also been evaluated in healthy volunteers in single dose up to 300 mg and repeated doses up to 150 mg (3 day-QD).

Considering the LFT elevations observed at 10 mg single dose (3 out of 8 patients in the Human Challenge Study) and at 75 mg single dose (5 out of 11 patients in the PoC extension study), and because causal relationship could not be established there is a need to further characterize the safety profile of the entire range of doses expected to be used as single doses or repeated dose in uncomplicated *P. falciparum* malaria.

As expected in a dose escalation sequential study, patients will be dosed initially at the lowest dose and be escalated in a stepwise manner. Single dosing is a necessary step to repeat dosing

and allows the detection and management of adverse events which may emerge or be more severe with repeated dosing.

The doses proposed in the newly added Cohort 5 and Cohort 6 are expected to be comparable or lower than the exposures which are considered to have acceptable safety and tolerability based on human and animal data (Table 3-2). In addition, the unbound exposure in patients (unbound fraction 0.08%) are expected to be much lower compared to healthy subjects (unbound fraction 0.15%) and dogs (unbound fraction 0.21%) (See KAE609 IB for further details).

Table 3-2 Estimated mean PK parameters in malaria patients for Cohort 5 and Cohort 6 in comparison with measured exposures in malaria patients and healthy subjects and preclinical toxicity studies

PK Parameter	50 mg single dose exposure in current study (Observed preliminary values)	110 mg** dose in patients (Estimated values)	150 mg dose in patients (Estimated values)	225 mg dose in patients (Estimated values)	Observed 300 mg dose in healthy subjects (Observed values)	IV 5 mg/kg/day for 14 days in dogs (Observed values)*	Oral 15 mg/kg/day for 3 days in dogs (Observed values)*
C _{max} (ng/mL)	810	1925	2625	3937	2090	33600	6200
AUC _{0-24h} (µg·h/mL)	12.4	37.4	50.9	76.5	36.0	55.9	119

The estimated exposures are calculated with reasonable assumption of linear pharmacokinetics of KAE609

*LOAEL (Lowest observed adverse effect level): Minimal to slight reversible adrenal findings

** A lower dose of KAE609 i.e. 110 mg may be selected for Cohort 6 based on the review of the liver safety data of Cohort 5 by a safety review committee.

Dose regimen for Coartem is in accordance with the product label.

3.4 Rationale for choice of comparator

The control treatment used in this study is Coartem, the artemisinin-based combination therapy artemether-lumefantrine. Coartem is widely used for *P. falciparum* malaria and has a well-characterized hepatic safety and efficacy profile (Hamed and Grueninger 2012). For these reasons, Coartem is considered the appropriate comparator treatment for this study.

3.5 Purpose and timing of interim safety review

Safety data will be reviewed by a safety review committee at predefined time points to decide about progression to the next cohort with the escalated doses (see Section 3.1).

In case safety data review is inconclusive for a particular cohort, number of patients in that cohort could be increased by up to 100% patients per treatment arm.

3.6 Risks and benefits

Based on the preclinical and clinical evaluation to date as presented in the IB for KAE609, it has been generally safe and well tolerated in patients up to single doses of 75 mg and repeated dose of 30 mg (3 day-QD) with the exception of reversible and asymptomatic LFT elevations observed with 10 mg single dose in human challenge study and 75 mg single dose in PoC extension study. Increase in LFT levels in earlier studies could have been influenced by the disease condition itself and/or the specific human challenge model. Hence, this study is being performed to characterize the hepatic safety profile of the expected dose range of KAE609 to be used in further development.

For newly added Cohort 5 and Cohort 6, single doses of 150 mg and 225 mg are proposed, respectively. PK exposure (AUC) of single dose 150 mg should be comparable to three doses of 50 mg once daily, already administered in this study and found to be safe and well tolerated during interim reviews (data not provided). Estimated AUC_{0-24h} for 225 mg dose would be >2 fold lower than the exposure which are considered safe based on oral dog toxicology study (15 mg/kg for 3 days) or comparable with 2 weeks IV toxicity study. The C_{max} is also expected to be around 1.7 fold lower than C_{max} observed in oral dog toxicology study (Table 3-2). Following ongoing review of the data of 150 mg dose if the safety events are found to be related to PK exposure, then dose of 110 mg may be studied to establish the exposure thresholds.

The risk to patients in this trial will be minimized by compliance with the eligibility criteria and study procedures, sequential dose escalation starting from the lowest strength of dose (10 mg), close clinical monitoring and minimal treatment duration (single dose evaluated before repeated dosing), and by the fact that dose-escalation will be carried out after the known peak time of LFT increases (i.e., 14 days) for KAE609. Patients will be hospitalized under close supervision until they are discharged by the investigator or designee on Study Day 4. To be discharged, patients should present 2 consecutive study assessments with negative blood smear and clearance of fever. At the discretion of the investigator, patients may remain in hospital for additional days if needed. Patients are advised to use commonly recommended precautions when in the sun (e.g. sunscreen, hat, protective clothing).

In the current study, KAE609 will be given to patients with uncomplicated symptomatic *P. falciparum* malaria. KAE609 is expected to reduce the number of circulating malaria parasites in the blood of patients and consequently improve their clinical symptoms within the first 24 hours. There is also the possibility of complete cure of their illness.

The risk of developing resistant strains of parasite is possible but low in this small study.

KAE609 has been earlier evaluated in adult patients with acute, uncomplicated malaria due to *P. falciparum* mono-infection at doses of 75 mg in a PoC extension study and 30, 20 mg, 15 mg and 10 mg in a Minimum Inhibitory Concentration (MIC) study (Hien et al 2017). In the MIC study, treatment failure due to recrudescence was reported in 4 (36%) patients and one patient had late treatment failure due to new malaria infection in the PoC extension study at 75 mg dose. There were no patients with early treatment failure (ETF) in the 30 mg and 15 mg dose groups while three patients from the 10 mg dose group (42%) and one patient from the 20 mg dose group (25%) were ETFs.

The risk of any treatment failure (see [Section 6.5.8](#)), recrudescence or new infection in this study will be managed with rescue medication in the form of standard-of-care pharmacotherapy (Coartem). This may minimize the likelihood of resistance emergence or spread of infection.

The current study will include only adult patients (≥ 18 years) suffering from uncomplicated symptomatic *P. falciparum* malaria. Given the expected sub-therapeutic efficacy of the doses of KAE609 in the first 2 cohorts, only a small number (N=10) of patients to assess safety events will be included (10 mg SD, 25 mg SD and 10 mg 3 Days). Following acceptable safety results in these cohorts, higher doses (25 mg 3 days and 50 mg SD or higher) with an increased number of patients (20 patients) will be enrolled in the study. Thereafter, the dose of KAE609 may be increased sequentially up to 225 mg based on continuous monitoring of safety.

This is the first time that KAE609 will be tested in African patients. All previous studies involved Asian and Caucasian participants only.

4 Population

The study population will consist of male and female patients (≥ 18 years old and ≥ 45 kg) with confirmed and uncomplicated symptomatic *P. falciparum* malaria.

Only patients with malaria symptoms and documented *P. falciparum* counts of 500 to 50 000 parasites/ μ l (assessed within 6 hours of screen visit) will be further screened for eligibility in the study. Routine microscopy data may be used as baseline parasite count for the protocol if the assessment was done within 6 hours and is compliant with protocol requirements.

The plan is to randomize approximately 210 patients in approximately 15 sites in malaria endemic countries.

A patient who enters screening but is determined not to be eligible to enter the treatment period will be considered a screen failure.

Rescreening of a patient who had failed screening assessments earlier in the study is allowed as per investigator discretion and/or after consultation with the sponsor.

4.1 Inclusion criteria

Patients eligible for inclusion in this study must fulfill all of the following criteria:

Demography

1. Male and female patients ≥ 18 years with a body weight ≥ 45 kg

Disease specific

2. Microscopic confirmation of acute uncomplicated *Plasmodium falciparum* using by Giemsa-stained thick film (refer to the laboratory manual for details)
3. *Plasmodium falciparum* parasitaemia of 500 to 50 000 parasites/ μ L

Health status

4. Axillary temperature $\geq 37.5^{\circ}\text{C}$ or oral/tympanic/rectal temperature $\geq 38.0^{\circ}\text{C}$; or history of fever during the previous 24 hours
5. Negative pregnancy test for patients of childbearing potential

Regulations

6. Written informed consent must be obtained before any study assessment is performed. If the patient is unable to write, then a witnessed consent according to local ethical standards is permitted
7. The subject is able to understand and comply with protocol requirements, instructions and protocol-stated restrictions and is likely to complete the study as planned
8. Living within reachable distance to the trial site to enable attendance for follow-up visits

4.2 Exclusion criteria

Patients fulfilling any of the following criteria are not eligible for inclusion in this study. No additional exclusions may be applied by the investigator, in order to ensure that the study population will be representative of all eligible patients.

Medical history and clinical status

1. Mixed *Plasmodium* infections
2. Signs and symptoms of severe malaria according to World Health Organization (WHO) 2016 criteria ([WHO 2016](#))
3. Active tuberculosis, or history of taking anti-tuberculosis medications within 12 months prior to screening
4. History of, or current alcohol misuse/abuse defined as five or more drinks on the same occasion on each of 5 or more days in the past 30 days
5. Known liver abnormalities, liver cirrhosis (compensated or decompensated), known active or history of hepatitis B or C (testing not required), known gallbladder or bile duct disease, acute or chronic pancreatitis
6. Clinical or laboratory evidence of any of the following:
 - AST/ALT > 1.5 x the upper limit of normal range (ULN), regardless of the level of total bilirubin
 - AST/ALT > 1.0 and \leq 1.5 x ULN and total bilirubin is > ULN
 - Total bilirubin > 2 x ULN, regardless of the level of AST/ALT
7. History of photodermatitis/increased sensitivity to sun
8. Known disturbances of electrolyte balance, e.g. hypokalemia, hypocalcemia or hypomagnesemia
9. Moderate to severe anemia (Hemoglobin level < 8 g/dL)
10. Any confirmed or suspected immunosuppressive or immunodeficient condition, including human immunodeficiency virus (HIV) infection
11. Severe malnutrition (Body Mass Index (BMI) < 16.0)
12. Severe vomiting, defined as more than 3 times in the 24 hours prior to inclusion in the study or severe diarrhea defined as more than 3 times watery stools per day
13. Pregnant or nursing (lactating) women
14. Sexually active patients not willing to practice effective contraception
15. Women of child-bearing potential, defined as all women physiologically capable of becoming pregnant, unless they are using highly effective methods of contraception during

dosing and for 30 days after administration of KAE609. Highly effective contraception methods include:

- Total abstinence (when this is in line with the preferred and usual lifestyle of the subject).
- Female sterilization (have had surgical bilateral oophorectomy with or without hysterectomy), total hysterectomy or tubal ligation at least six weeks before taking investigational drug. In case of oophorectomy alone, only when the reproductive status of the woman has been confirmed by follow up hormone level assessment.
- Male sterilization (at least 6 months prior to screening). For female subjects on the study, the vasectomized male partner should be the sole partner for that subject.
- Use of oral, injected or implanted hormonal methods of contraception or placement of an intrauterine device (IUD) or intrauterine system (IUS) or other forms of hormonal contraception that have comparable efficacy (failure rate < 1%), for example hormone vaginal ring or transdermal hormone contraception. Coartem/Riamet may reduce the effectiveness of hormonal contraceptives. Therefore, patients randomized to Coartem using oral, transdermal patch, or other systemic hormonal contraceptives should be advised to use an additional non-hormonal method of birth control.
- In case of use of oral contraception women should have been stable on the same pill for a minimum of 3 months before taking investigational drug.
- Women are considered post-menopausal and not of child bearing potential if they have had 12 months of natural (spontaneous) amenorrhea with an appropriate clinical profile (e.g., age appropriate, history of vasomotor symptoms) or have had surgical bilateral oophorectomy (with or without hysterectomy), total hysterectomy or tubal ligation at least six weeks ago. In the case of oophorectomy alone, only when the reproductive status of the woman has been confirmed by follow up hormone level assessment is she considered not of child bearing potential.

Periodic abstinence (e.g., calendar, ovulation, symptothermal, post-ovulation methods) and withdrawal are not acceptable methods of contraception.

16. Sexually active males must use a condom during intercourse while taking drug and for at least 30 days after stopping the study medication and should not father a child in this period. A condom is required to be used also by vasectomized men in order to prevent delivery of the drug via seminal fluid
17. Patients with a family history of congenital prolongation of the QTc interval or sudden death or with any other clinical condition known to prolong the QTc interval such as patients with a history of symptomatic cardiac arrhythmias, with clinically relevant bradycardia or with severe cardiac disease
18. Patients taking drugs that are known to prolong the QTc interval
19. Resting QTcF > 450 ms (males), QTcF > 460 ms (females) at screening
20. Any surgical or medical condition which might significantly alter the absorption, distribution, metabolism, or excretion of drugs, or which may jeopardize the subject in case of participation in the study. The investigator should make this determination in consideration of the patient's medical history, clinical and/or laboratory results.

21. History of malignancy of any organ system (other than localized basal cell carcinoma of the skin or *in situ* cervical cancer), treated or untreated, within the past 5 years, regardless of whether there is evidence of local recurrence or metastases
22. Known chronic underlying disease such as sickle cell disease, and severe cardiac impairment.
23. Patients with serum creatinine $\geq 2 \times$ ULN in the absence of dehydration. In case of dehydration, patients with serum creatinine $\geq 2 \times$ ULN after oral or parenteral rehydration.
24. Inability to tolerate oral medication, to drink.
25. Patients taking any drug which is metabolized by the cytochrome (CYP) 2D6 enzyme (e.g., flecainide, metoprolol, imipramine, amitriptyline, clomipramine).
26. Patients taking drugs that are strong inducers of CYP3A4 such as rifampicin, carbamazepine, phenytoin, St. John's wort (*Hypericum perforatum*)
27. Known hypersensitivity to any of the agents used in the study

Interfering substances

28. Patients with prior antimalarial therapy or antibiotics with antimalarial activity within less than five (5) plasma half-lives (or within 4 weeks of screening if half-life is unknown)
29. Patients with prior herbal medication within one week of screening
30. Use of other investigational drugs within 5 half-lives of enrollment, or within 30 days or until the expected pharmacodynamic (PD) effect has returned to baseline, whichever is longer
31. Patients taking medications prohibited by the protocol (see [Section 5.5.8](#), [Appendix 4](#))
32. Previous participation in any malaria vaccine study or received malaria vaccine in any other circumstance

5 Treatment

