Based on the pre-specified criteria (Table 3-1) and the review of the liver safety data by a safety review committee, the recruitment in Cohort 5 may be stopped and a lower dose of KAE609 i.e. 110 mg may be selected for Cohort 6.

The study could be stopped after Cohort 5 if there is no added advantage for dosing the patients with 225 mg single dose from the perspective of future clinical development of KAE609 and its subsequent use in clinical practice.

Figure 3-1 Study KAE609A2202 diagram

Given the expected sub-therapeutic efficacy of the doses of KAE609 in the first 2 cohorts, a smaller number (N=10) of patients will be included (10 mg Single Dose (SD), 25 mg SD and 10 mg 3 Days) to detect potential LFT increases. In the subsequent cohorts a higher number (N=20) of patients will be included. All patients will be followed up for 4 weeks with close monitoring in an inpatient setting for at least the first 3 days (Study Day 4) for efficacy and safety followed by outpatient monitoring up to Study Day 29.

Patients will remain in the hospital under close supervision until they are discharged by the investigator or designee on Study Day 4. To be discharged, patients should present 2 consecutive study assessments with negative blood smear for *P. falciparum* parasites and clearance of fever. At the discretion of the investigator, patients may remain in hospital for additional days if needed.

Coartem® (Artemether-Lumefantrine) will be used as rescue medication in KAE609 patients meeting the treatment failure criteria (see Section 5.5.6). Any patient on KAE609 who does not need rescue medication up to Study Day 28 will be given Coartem at the end of the study (Study Day 29) and will be followed as per standard medical care.

Visits to assess safety and efficacy will be scheduled during the follow-up period as described in the assessment schedule table (Table 6-1). If malaria symptoms re-emerge outside the scheduled study visits, patients will be instructed to contact the investigator as soon as possible. For severe malaria, rescue medication according to local guidance will be used.

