5.5.4 Instructions for prescribing and taking study treatment

KAE609

KAE609 can be administered irrespective of the timing of food intake.

Study medication will be administered by the study center personnel with approximately 180-240 ml of water. Each subject's mouth must be checked to ensure that the medication was swallowed. In the case that the patient vomits within 30 minutes of intake a replacement dose will be given to the patient and the investigator or designee will notify IRT. If the second dose is vomited the patient has to be given Coartem as rescue medication.

Coartem

Patients will be dosed BID for 3 days (at the following time points: 0, 8, 24, 36, 48, and 60 hours) and must receive a standard meal within 30 min prior to dosing, as per label. In the case that the patient vomits within 1 hour of intake a replacement dose will be given to the patient and the investigator or designee will notify IRT. If the second dose is vomited the patient has to be given non-lumefantrine standard of care.

Conventional 80/480 mg tablets or 20/120 mg tablets are to be taken orally with a glass of water. The dispersible tablet is to be dissolved in 10 mL of water in a small cup, and subsequently administered orally under hospital supervision; thereafter the cup will be rinsed with an additional 10 mL of water and the content is to be swallowed again.

Coartem medication should be followed whenever possible by food/drink (broth, sweetened condensed milk, etc.) as appropriate.

All dosages prescribed and dispensed to the subject during the study must be recorded on the Dosage Administration Record (DAR) CRF.

All kits of study treatment assigned by the IRT will be recorded in the IRT.

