5.5.6 Rescue medication

The following circumstances warrant discontinuation of study treatment and the implementation of rescue medication (see [Section 6.5.8](#)):

Early treatment failure (ETF)

ETF is defined within this protocol as:

1. Clinical decline or lack of improvement (per Investigator) at 24 hours after first dose of treatment.
2. Development of any clinical complications (described in the WHO definition of complicated/severe malaria (WHO Guidelines 2010)) in the presence of parasitaemia within 72 hours of the first dose of treatment
3. Parasitaemia $> 75\ 000/\mu\text{L}$ at or after 12 hours post-dose
4. Parasitaemia \geq baseline with or without fever at 36 hours after first dose of treatment
5. Any parasitaemia based on microscopy with fever, 48 hours post-dose
6. Parasitaemia $> 100/\mu\text{L}$ based on microscopy with or without fever, 72 hours post-dose

Late Clinical Failure (LCF)

Development of danger signs or severe malaria on any day between Study Day 5 and Day 29 in the presence of parasitaemia without previously meeting any of the criteria of ETF.

Presence of parasitaemia and axillary temperature $\geq 37.5^\circ\text{C}$ on any day between Study Day 5 and Day 29 without previously meeting any of the criteria of ETF.

Late Parasitological Failure (LPF)

Presence of parasitaemia on any day between Study Day 5 and Day 29 and axillary temperature $< 37.5^\circ\text{C}$ without previously meeting any of the criteria of ETF or LCF.

Commencement of rescue medication with Coartem may occur after start of trial medications and up to Study Day 28 as deemed necessary by the investigator. Any patient on KAE609 who

did not need rescue medication up to Study Day 28, will be given Coartem at end of the study at Study Day 29. Rescue medication according to local guidance will be used for severe malaria.

Patients randomized to Coartem and meeting treatment failure definition will be further treated by rescue medication as per local treatment guidance.

The patients receiving rescue medication will not be replaced and will not discontinue the study (i.e., all the examinations as per the assessment schedule and all CRF pages for this patient will need to be completed).

Safety blood tests (Full Blood Count (FBC) and blood chemistry) will be collected on the initial day of rescue medication dosing. Blood films and blood sampling for parasite count and genotyping must be taken before giving the rescue treatment.

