5.5.8 Prohibited medication

Use of the following treatments is NOT allowed as per below recommendation in **KAE609 Cohorts**:

- Antimalarials other than the study drug and rescue medication (Coartem) are not permitted during the entire study period.
- Herbal medication should not have been taken within 1 week before the study treatment is given and should be avoided until the last study visit.
- Any other investigational treatment for the whole study duration.
- KAE609 undergoes CYP3A4 metabolism thus potent and moderate CYP3A inhibitors (such as HIV antivirals: e.g., ritonavir miscellaneous: e.g., clarithromycin, itraconazole, ketoconazole, grapefruit juice, verapamil, cimetidine) and inducers (such as HIV antivirals: e.g., efavirenz miscellaneous: e.g., barbiturates, carbamazepine, phenytoin, rifampin, St. John's wort) are not allowed up to 14 days before enrolment in the study or minimum 5 half-lives of the perpetrator drug (whichever is longer) administration and up to 7 days post administration.
- KAE609 is a potent inhibitor of CYP2C19 and can potentially increase the exposure of drugs which are a substrate of CYP2C19 by many folds (such as Proton pump inhibitors: e.g., lansoprazole, omeprazole, anti-epileptics: e.g., phenytoin, miscellaneous: e.g., amitriptyline, chloramphenicol, clomipramine, indomethacin, nelfinavir, progesterone (synthetic progestins used in hormonal contraceptives are not prohibited since they are metabolized by CYP3A4), proguanil, propranolol, warfarin). Therefore, these are prohibited for the treatment duration and 7 days after last dose.
- Drug known to cause QTc prolongation or known to be potentially hepatotoxic (see [Appendix 4](#)) are prohibited for the treatment duration and 7 days after last dose.

Apart from the above mentioned possible interactions in vitro data suggest KAE609 is inhibitor of CYP2B6, CYP2C9, CYP2A6, CYP1A2, CYP2D6, CYP2C8, and CYP3A4, however, assessment including SimCYP simulation suggests that potential change in the exposure of drug substrate of any of these would be less than two fold and unlikely to be of clinical significance. Nonetheless caution should be exercised such as staggering the dose of victim drug by ~12 hours from last dose of KAE609.

Use of the following treatments is NOT allowed as per below recommendation in **Coartem/Riamet Cohorts**:

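### Criterion 15 advises an extra non-hormonal contraceptive method only for patients randomised to Coartem, although KAE609 patients are also due to receive Coartem inside their 30-day contraception period

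*Protocol*

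**What the plan says.** Protocol section 4.2, criterion 15, excludes women of child-bearing potential unless they use highly effective contraception during "dosing and for 30 days after administration of KAE609". The accepted methods include "Use of oral, injected or implanted hormonal methods of contraception", as well as rings and transdermal products, and are not limited by arm. The same bullet warns that "Coartem/Riamet may reduce the effectiveness of hormonal contraceptives" and then says that "patients randomized to Coartem using oral, transdermal patch, or other systemic hormonal contraceptives should be advised to use an additional non-hormonal method" of birth control.

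Other sections plan Coartem for patients assigned to KAE609:

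- **Section 5.5.6, rescue:** "Commencement of rescue medication with Coartem may occur after start of trial medications and up to Study Day 28".
- **Section 5.5.4, vomiting of KAE609:** "If the second dose is vomited the patient has to be given Coartem as rescue medication".
- **Section 3.1, end of study:** "Any patient on KAE609 who does not need rescue medication up to Study Day 28 will be given Coartem" on Study Day 29.

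Section 5.5.8, in the part for the KAE609 cohorts, confirms that "synthetic progestins used in hormonal contraceptives are not prohibited since they are metabolized by CYP3A4".

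**The concern.** The advice is justified by what Coartem does to hormonal contraception. That does not depend on whether a woman takes Coartem as her randomised treatment, as rescue or at the end of the study. Yet the advice is limited by randomised arm.

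The woman left out is the one for whom the 30-day period was set, because criterion 15 ties that period to KAE609. A site that follows section 4.2 exactly could give her Coartem while she relies on a hormonal method, without the precaution a comparator patient receives for the same drug. At stake is an avoidable weakening of contraception after exposure to an investigational drug for which section 10.2 warns of unknown fetal risk.

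**Working it through.** No power or sample-size figure bears on this point. The check is study-day arithmetic plus a search for text elsewhere that would close the gap.

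**Inputs**

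- The first treatment day is Study Day 1 (Protocol 6.5.8, note).
- The last KAE609 dose falls on Day 1 for single-dose arms and Day 3 for 3-day arms (Table 5-1).
- The contraception period runs for 30 days after KAE609 (4.2, criterion 15), counted here from the last dose.
- Coartem may reach KAE609 patients from the start of treatment to Day 28 as rescue, or on Day 29 (3.1, 5.5.4, 5.5.6).
- Coartem dosing times are 0, 8, 24, 36, 48 and 60 hours (5.5.4). These are stated for the comparator arm and assumed here to apply to the Day 29 course as well.

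**End of the KAE609 contraception period** = day of last dose + 30

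- Single dose: 1 + 30 = Day 31
- 3-day regimen: 3 + 30 = Day 33

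**Days still to run when Coartem starts** = end of period − Coartem start day

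| Coartem starts | Single dose | 3-day regimen |
|---|---|---|
| Day 29 (end of study) | 31 − 29 = 2 | 33 − 29 = 4 |
| Day 28 (latest rescue) | 31 − 28 = 3 | 33 − 28 = 5 |
| Day 4 (72-hour failure criterion) | 31 − 4 = 27 | 33 − 4 = 29 |
| Day 1 (replacement dose vomited) | 31 − 1 = 30 | – |

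Every planned start falls inside the period. A course begun on Day 29 ends 60 hours later, on Day 31, so for single-dose patients it covers all the days that remain.

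**Who could be affected.** Planned KAE609 patients: 3 arms × 10 + 6 arms × 20 = 30 + 120 = 150. The other 210 − 150 = 60 are randomised to Coartem. The 150 is a ceiling that includes men and women not using systemic hormonal methods. The advice for Coartem patients came in with Amendment 3, whose rationale says that doses up to those of Cohort 4 had already been reviewed. The patients still to be enrolled under it are therefore probably the 2 × 20 = 40 planned KAE609 patients of Cohorts 5 and 6, all single dose, with a period ending on Day 31.

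**Does other text close the gap?**

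- Section 5.5.8 says to follow the Coartem prescribing information, but only in the part for the Coartem/Riamet cohorts.
- Sections 5.5.4, 5.5.6 and 5.6.2, which govern rescue, do not mention contraception.
- Criterion 14 and section 10.2 require effective contraception and adherence to the contraception requirement. Neither mentions the Coartem interaction.
- The urine pregnancy test at study end (6.5.6) detects a pregnancy but does not advise on preventing one.

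None of these gives the advice to a KAE609 patient.

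**The case against.** The strongest case on the other side is about weight; the text itself is not in dispute.

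Most KAE609 patients would meet Coartem only on Day 29, with 2 or 4 days of the period left. The documents give neither the onset nor the duration of Coartem's effect, so a real loss of protection in those days cannot be shown from them. This stands, and it makes early rescue the stronger case. Early failure is foreseeable: section 3.6 reports early treatment failure in three patients (42%) at 10 mg in an earlier study. That figure concerns the lowest dose, however, and should not be carried over to Cohorts 5 and 6.

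The 30-day figure belongs to a patient who vomited both her dose and its replacement, so her KAE609 exposure is the least certain of all. That also stands; the Day 4 row is the better guide to what matters.

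Coartem is a marketed product with a label, and patient information may already carry the advice. Amendment 3 states that its changes affect the model consent, and consent pages are not in the review copy. What patients are actually told therefore cannot be checked. This limits the finding to the protocol text, but it does not repair a criterion that names the wrong group.

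Finally, an eligibility criterion is applied before randomisation, whereas rescue is decided under 5.5.4 and 5.5.6. Repeating the advice there would be useful but is optional, because criterion 15 worded by receipt of Coartem already covers rescue and Day 29 use.

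**Conclusion.** The concern holds. Criterion 15 limits a precaution by randomised arm when the stated reason for it is exposure to Coartem. The protocol plans that exposure for nearly every KAE609 patient, inside the KAE609 contraception period. The exceptions are severe malaria rescued by local guidance and patients who leave the study.

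The remaining period when Coartem starts is 2 to 4 days for end-of-study Coartem and 27 to 29 days for rescue on Day 4. This rests on counting the 30 days from the last KAE609 dose. The statement that the Day 29 course fills the remaining single-dose period also assumes the comparator dosing schedule. No duration of reduced contraceptive protection is claimed, and the number of affected women is unknown.

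This is a narrow patient-safety gap in the wording. It should be corrected, but it touches no endpoint, sample size or analysis.

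**What to change.** In section 4.2, criterion 15, replace the restriction to patients randomised to Coartem with: *patients receiving Coartem in the study (randomized, rescue or Day 29)*. Leave the rest of the sentence as it is. Check that the patient information says the same. A short reminder in 5.5.4 and 5.5.6, where rescue is decided, is optional.

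The cost is one phrase and one extra piece of advice to KAE609 patients who use systemic hormonal contraception. No visit, procedure or exclusion is added. As with any protocol change, section 11.1 requires a written amendment with sponsor and ethics approval, and health-authority approval where required. The patient information may also need revision if it repeats the restriction.
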